##### **Design and Procedural Details of Aim/Phase 2:** (also see Figure 2 for Timeline)

###### **Step 1) Deliver VAX-MOM training/intervention to randomized practices:**

###### Randomization Details:

Practices will be the unit of randomization. We will assign practices using a covariate constrained randomization strategy as follows: First, we will use data from Aim #1 to obtain key factors that we expect to affect the primary outcomes. We will perform constrained randomization to allocate practices within each health system to intervention/control arms and ensure each arm has similar baseline flu and Tdap vaccination rates, percent of patients covered by Medicaid, number of OB providers, and number of patients. Specifically, we will use these variables to construct and evaluate a balance criterion, which is the sum of the squared difference between standardized group means on these variables. We will generate randomization separately by health system. We will generate all possible combinations of eligible practices in 2 arms (using a SAS macro), and define an acceptable set of randomizations that result in balanced variables (generally the lowest 10% on the balance criterion). From this set of randomizations, we will select one set at random, and then randomly assign each practice to intervention vs control group.

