### **Figure 2: Timeline of Aim/Phase 2 Study Procedures**

## 5. SUBJECT POPULATION

During aim/phase 2, we will utilize subjects from a total of 37 participating practices across both NY and CA. “Subjects” refers to both a) the providers, nurses, and staff at the participating OB/GYN practice sites and b) data from practice patients (pregnant women) gathered via electronic health record (EHR). A list of all participating practices and corresponding demographic information is below (Table 6).

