**Table 6: Participating Practice Sites and Demographic Information (Total Subject Pool)**

NEW YORK PRACTICES:		
Participating Practice	Total Number of Providers	Annual Deliveries
[REDACTED]	35	800
[REDACTED]	9	100
[REDACTED]	12	200
[REDACTED]	18	300
[REDACTED]	16	500
[REDACTED]	2	200
Insurance (% Private/Public/Other)	45/55/5	
Race/Ethnicity (% White/ Black/Hispanic)	65/25/10	
CALIFORNIA PRACTICES:		
Participating Practice	Total Number of Providers	Annual Deliveries
[REDACTED]	10	511
[REDACTED]	4	130
[REDACTED]	6	144
[REDACTED]	3	13
[REDACTED]	7	415
[REDACTED]	4	110
[REDACTED]	4	17
[REDACTED]	3	0
[REDACTED]	5	256
[REDACTED]	1	16
[REDACTED]	5	392
[REDACTED]	6	353
[REDACTED]	3	309
[REDACTED]	3	298
[REDACTED]	6	143
[REDACTED]	3	128
Insurance (% Private/Public/Other)	55/45/5	
Race/Ethnicity (% White/ Black/Hispanic)	65/15/20	

CALIFORNIA PRACTICES:		
Participating Practice	Total Number of Providers	Annual Deliveries
[REDACTED]	13	1792
[REDACTED]	8	300
[REDACTED]	8	1500
[REDACTED]	5	157
[REDACTED]	1	80
[REDACTED]	4	472
[REDACTED]	2	180
Insurance (% Private/Public/Other)	89/1/10	
Race/Ethnicity (% White/ Black/Hispanic)	52/7/13 & 14% Asian	
[REDACTED]		
Participating Practice	Total Number of Providers	Annual Deliveries
[REDACTED]	5	≈800
[REDACTED]	7	≈1000
[REDACTED]	3	≈450
[REDACTED]	3	≈450
[REDACTED]	2	≈250
[REDACTED]	1	≈150
[REDACTED]	9	≈1000
[REDACTED]	3	≈500
Insurance (% Private/Public/Other)	20/75/5	
Race/Ethnicity (% White/ Black/Hispanic)	15/25/55 & 5% Asian	

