## 17. DATA ANALYSIS PLAN

Primary outcomes (receipt of Flu and Tdap vaccines) are binary and our main explanatory variable will be an indicator for study arm. We will employ intent-to-treat analyses using generalized linear mixed models (GLMMs) with practice random effects, an approach recommended for group-randomized RCTs in which the goal is to estimate the causal effects of interventions on individuals, adjusted for clustering within groups. This method performs well in situations where the number of observations per cluster is large and for unequal cluster sizes. Models will assume a binomial distribution and a log link function in order to compare vaccination rates between study arms in terms of risk ratios. We will adjust for all practice-level variables included in the randomization balancing criterion, as well as patient-level race/ethnicity (and prior year vaccination status for the flu analysis). Hypothesis tests will be two-sided with alpha = 0.025, reflecting a 2-fold Bonferroni correction for the co-primary endpoints of Flu and Tdap vaccination status, ensuring a familywise type I error rate of 0.05. Analyses will be performed using SAS v. 9.4 (SAS Institute Inc., Cary, NC).

Power Analysis: We assume national vaccine rates for flu (49%) and Tdap (54%). Adjusting for clustering of patients in practices, and assuming an intraclass correlation (ICC) of 1% (consistent with previous work), this sample size provides >80% power to detect an overall increase of 6.3 percentage point increase in vaccination rates between the QI intervention and control arms. This assumes a chi-squared test (a simplification of the planned mixed model analysis described above), a test-level alpha of 0.025, and a sample size of 5,000 pregnant women organized into 16 practices per study arm.

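### The stated >80% power for 6.3 points assumes equal practices and a normal reference; with Table 6's practice sizes and a practice-level t test it is about 73–79% before any covariate gain

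*Combined protocol and SAP*

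**What the plan says.** Section 17 (Data Analysis Plan, Power Analysis) takes control rates of 49% (flu) and 54% (Tdap), an ICC of 1% and a test-level alpha of 0.025. It states that the sample "provides >80% power to detect an overall increase of 6.3 percentage point increase" in vaccination rates, with "a sample size of 5,000 pregnant women organized into 16 practices per study arm". It describes the underlying chi-squared test as a simplification of the mixed model that will be fitted.

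On the analysis, Section 17 plans a binomial mixed model with a log link and a random effect for practice, and remarks: "This method performs well in situations where the number of observations per cluster is large and for unequal cluster sizes". It adds: "We will adjust for all practice-level variables included in the randomization balancing criterion". Section 4 (Randomization Details) lists those variables: "similar baseline flu and Tdap vaccination rates, percent of patients covered by Medicaid, number of OB providers, and number of patients". The Bonferroni split is described as "ensuring a familywise type I error rate of 0.05". Section 17 names no estimation method, reference distribution or denominator degrees of freedom.

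Section 5 says "we will utilize subjects from a total of 37 participating practices across both NY and CA", and Table 6 gives the annual deliveries of each.

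**The concern.** Two things that lower power in a practice-randomised trial are absent from the power calculation.

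- **Unequal practice sizes.** At a fixed total number of women and practices, unequal sizes reduce the effective sample, even when a mixed model weights practices well. The remark that the method copes with unequal clusters concerns how the estimator behaves. It does not put the lost information back into the power figure.
- **Few practices.** Arm is a between-practice effect, estimated from 36 or 37 practices with five practice-level covariates. A normal critical value is too small for such a test.

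The second point also affects error control. If the variance is estimated by maximum likelihood or the test uses a normal reference, each co-primary test may exceed its 0.025, and the familywise 0.05 rests on that level.

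**Working it through.** **Inputs.** From Section 17: p = 0.49 or 0.54, difference 0.063, ICC 0.01, two-sided alpha 0.025, 5,000 women and 16 practices per arm. From Table 6: 37 practices, total 14,416 deliveries, mean 390, coefficient of variation 1.02 (1.00 over the 36 non-zero practices; one lists 0). Assumption: annual deliveries stand in for women analysed.

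**1. Reproducing the plan's figure.** Equal practices have 5,000/16 = 312.5 women.
- Design effect = 1 + (312.5 − 1) × 0.01 = 4.115.
- Effective n per arm = 5,000/4.115 = 1,215.
- Flu: SE = √[(0.49×0.51 + 0.553×0.447)/1,215] = 0.02023. Power = Φ(0.063/0.02023 − 2.241) = 80.9%.
- Tdap: SE = 0.02004. Power = 81.7%.

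The plan's figure is therefore the equal-size, normal-reference calculation. Reading 5,000 as the total over both arms gives only about 71–72% and does not reproduce it.

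**2. Table 6 sizes in the planned mixed model.** Effective n per arm = ½ Σ m/[1 + (m − 1) × 0.01] over the practices.
- Sizes scaled by 10,000/14,416, which keeps Section 17's number of women: 1,115.
- Sizes as listed: 1,234.

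**3. Reference distribution.** Practice-level degrees of freedom are 37 − 2 − 5 = 30, and the critical value rises from 2.24 to 2.36. Power uses the noncentral t.

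| Power for 6.3 points (flu / Tdap) | Effective n per arm | Normal | t, 30 df |
|---|---|---|---|
| Equal practices, 32 (as in the plan) | 1,215 | 80.9 / 81.7% | 77.1 / 77.9% |
| Table 6 pattern, 10,000 women | 1,115 | 77.1 / 78.0% | 73.1 / 74.0% |
| Table 6 as listed, 14,416 women | 1,234 | 81.5 / 82.3% | 77.8 / 78.6% |

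Counting 36 practices (29 df) changes the t figures by at most 0.2 points. Not deducting the five covariates (34 df) gives 73.6 / 74.5% and 78.3 / 79.1%. Keeping Section 17's 32 practices and 5,000 women per arm, with the size pattern of Table 6, gives an effective n of about 1,027 per arm and 69–70% (t, 30 df).

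**4. Detectable difference at 80% power (t, 30 df).** 6.7–6.8 points with 10,000 women; 6.4–6.5 points with 14,416.

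**5. Covariate gain needed.** Solving for the ICC that gives 80% with t on 30 df: 0.0080 (flu) and 0.0082 (Tdap) with 10,000 women, a fall of 18–20%; 0.0093 and 0.0096 with 14,416 women, a fall of 4–7%.

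**6. The chi-squared simplification on the same sizes.** An unweighted comparison has design effect 1 + (Σm²/Σm − 1) × 0.01 = 6.44 (10,000 women) or 8.85 (14,416). Effective n per arm is 776 or 814, and power is 60–61% or 62–63%. The simplification is thus not a conservative stand-in once sizes vary.

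**7. Type I error at nominal 2.5% per test.** This was simulated on practice means with normal errors: 36 practices split within the four health systems, practice size plus four random practice-level covariates, 20,000 null trials per scenario (Monte Carlo standard error √(0.025×0.975/20,000) = 0.11 points).

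| Estimation | Normal reference | t, 29 df |
|---|---|---|
| ML | 5.7–6.3% | 4.6–5.1% |
| REML | 3.4–3.5% | 2.7% |

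**The case against.** The strongest reply has four parts.

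- **On Table 6 as listed, size variation costs nothing against the stated figure.** The effective sample of 1,234 exceeds the plan's 1,215, because the extra practices and women offset the unequal sizes. At full volume the shortfall comes entirely from the t reference. This is correct. The 73–74% end needs the sizes scaled down to 10,000 women, a combination that no section describes as such; it joins Section 17's total to Table 6's pattern. But Section 17 commits to that total, and a t-type reference is what a test on so few practices needs.
- **Covariates are charged but not credited.** Degrees of freedom are deducted for baseline practice rates while their variance reduction is set to zero. At full volume a 4–7% cut in the ICC would restore 80%. This also stands: 73–79% is a no-gain figure. However, the deduction itself costs only about half a point, and the documents quantify no gain.
- **The simulation is an approximation.** It does not reproduce the binomial log-link model or the constrained randomisation, and the plan does not say that it will use ML. The exact rates should not be carried over. The plan allows any of the four combinations, though, and they differ materially.
- **The plan openly calls its calculation a simplification, and the shortfall is modest.** Both are true, and they limit the weight of the point. The label does not supply the missing allowance.

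**Conclusion.** The concern holds. The arithmetic behind the stated power is right for equal practices and a normal reference, but Table 6 contradicts the first assumption and the number of practices makes the second optimistic. Without covariate gain, and with a practice-level t reference, power for 6.3 points is about 73–74% (10,000 women) to 78–79% (14,416 women), roughly 1 to 7 points below 80%.

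This rests on the plan's ICC of 1% and on annual deliveries representing the women analysed. Sections 4 and 6 describe a 2021–2022 extract, and the women eligible for each vaccine could be more or fewer than Table 6 implies. A modest covariate gain could close the gap, so the trial is not shown to be underpowered; the claimed figure is unsupported as written. Separately, the missing estimation method and degrees of freedom leave the 0.025 per test unprotected. The size of that risk comes from a linear approximation and is indicative only. The point is worth correcting but does not threaten the design.

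**What to change.** 1. Restate power for the planned mixed model from Table 6's sizes, giving the number of practices (Section 17 uses 32, Section 5 says 37, and one lists no deliveries), the women analysed and the reference distribution. Without covariate gain this is 73–74% to 78–79% for 6.3 points, or a detectable difference of about 6.4–6.8 points at 80% power.
2. If a covariate gain is assumed, state the reduced ICC and its source. The Aim 1 baseline data could supply it.
3. In the primary analysis, state that arm is tested with REML-type estimation and denominator degrees of freedom based on the number of practices (Kenward-Roger or between-within).

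The cost is SAP wording only, with no extra practices or women. The stated power becomes slightly less favourable, and the critical value rises from 2.24 to about 2.36.

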### Final Time/Cost Analysis:

Upon completion of aim/phase 2 we will conduct a final time/cost analysis. Our two-fold cost measures are (a) total intervention cost to implement the VAX-MOM program aggregated at the four health-system level under a cost analysis and (b) cost per additional flu or Tdap vaccination under a subsequent cost-effectiveness analysis. To derive a policy implication regarding the sustainability of programs, we will estimate costs and ICER estimates from the health system perspective.

**Total Cost:** To make these cost measures comparable to similar past interventions of reminders and educational programs, we will estimate cost with one-year time horizon, excluding the cost to purchase, store and administer vaccines. We will estimate the total intervention cost, summing non-personnel costs (e.g., EHR hardware, software, and materials) and personnel costs. The personnel costs will distinguish research costs from intervention costs (e.g., practice-level meeting and collecting EHR data). The dollar values of these personal costs will be calculated by multiplying “time efforts” (weekly reported by study personnel using a REDCap email survey) with the nationally representative “hourly-wage rates” by occupation codes of study personnel, derived from the Bureau of Labor Statistics.

**Cost-Effectiveness:** We will develop a standard decision model for our cost-effectiveness analyses. The effectiveness measures are the rates of flu and Tdap vaccination estimated under Aim 2b.

As explained above, this intervention cost will exclude the cost to purchase, store and administer vaccines, which is assumed to be identical among all practices. Applying the same assumption, the average cost for the control group (costControl) is zero. To make separate ICER estimates for flu and Tdap vaccination, the Tdap-vaccination-specific costStudy will be estimated during non-flu season (April to September) first and applied for calculating the flu-vaccination-specific costStudy during a flu season (October to March), assuming the Tdap-vaccination-specific costStudy is constant throughout a year. Using the developed standard decision model, we will conduct probabilistic analyses to generate point estimates and 95% CIs for ICERs and one-way sensitivity analyses to determine conditions for being lower than the thresholds of cost-effectiveness, e.g., healthcare-system based quality improvement interventions to improve flu vaccination uptake targeting general populations (median ICER \$51 among 23 interventions) and healthcare workers (median ICER \$125 among 6 interventions) reported by a systematic review.

Hyp. : Cost per additional flu or Tdap vaccination under the VAX-MOM is lower than past similar interventions.

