**Table 5. EHR Data Extraction Categories**

Primary	

• Flu vaccines received during flu season (Sept-April)

• Tdap vaccines received during 27-36 weeks of pregnancy

Secondary	

• Vaccine refusal (as documented in EHR)

• Missed opportunities for flu and Tdap

• Flu vaccine in prior season

• Covid vaccination

Patient Demographics	

• Race/ethnicity

• Age

• Insurance

• Language

• Parity

Practice Demographics	

• Site

• Provider type (resident, midwife, MD)

- Measure Procedures

Each health system [REDACTED] will have its own “report builder.” The report builder will be in charge of collecting the electronic health record (EHR) data from their own health system and putting it into a format (report) that can be easily understood and analyzed by study staff.

*Bi-Monthly Feedback Reports:* The report builder for each health system will create vaccine rate feedback reports utilizing extracted EHR data for intervention sites on a bi-monthly basis. These reports will be sent either via secure e-mail directly to the study coordinator in each corresponding state, or uploaded to the secure shared Box folder. The study coordinator will then disseminate the vaccination rates for each site to all corresponding site personnel.

For NY health systems, in the event an automated EHR feedback report cannot be generated in time for any given month, the identified vaccine champions or study personnel will estimate flu and Tdap vaccine rates via manual chart review. All vaccine champions and/or study personnel conducting manual chart review will have completed all appropriate eRecord training prior to accessing patient charts. Of those patients who delivered during the identified month, at least 20% will be reviewed. For each chart reviewed, the vaccine champion or study personnel will document the receipt (or lack thereof) of influenza and Tdap immunization as well as Covid vaccination when possible, and will share results with the study team via secure e-mail.

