#### **Step 4) Evaluate cost of the VAX-MOM intervention:**

[figure not shown]
Practice Time & Cost Survey (see “*PracticeTime&CostSurvey...*” document): A survey aimed at evaluating the amount of time and money devoted to VAX-MOM intervention activities will be sent by the study coordinators via REDCap to the vaccine champion for each site on a monthly basis. The survey will be completed by the vaccine champion using their best time/cost estimates pertaining to the month prior.

Study Staff Time & Cost Survey (see “*StudyStaffTime&CostSurvey...*” document): A survey aimed at evaluating the time and cost efforts of VAX-MOM study staff will be sent to study personnel on a weekly basis via REDCap.

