#### **Site Personnel Consent:**

##### **Delivery of Training Content & Involvement in 12-Month QI Intervention**

*(All site personnel: completion of e-learning module, attendance of follow-up site meeting, and participation in monthly/bi-monthly discussions of rate feedback and PDSA cycles)*

This study involves commonly accepted quality improvement efforts aimed to improve upon the standard of care in medical settings, such as the completion of e-learning modules and in-person trainings specifically related to practice goals, the review of practice metrics (vaccine rates) by site personnel, discussion of office workflow procedures/efficacy, and trainings in optimal communication techniques.

We are therefore seeking a *waiver of documentation of consent and a waiver of HIPAA authorization* for the training portion of the study. More specifically, we are requesting this waiver because: **a)** the training portion of the study is no

greater than minimal risk, **b)** the purpose of the study/intervention and a basic framework of the trainings will be clearly outlined for participants in the Information Sheet (see “*InformationSheetTrainingPhase...*” document) e-mailed to them at the onset of the intervention phase, **c)** ample time will be given to personnel to review the Information Sheet in full and ask questions of study staff regarding the quality improvement effort and/or specific tasks involved in the training phase, and **d)** PHI will not be reused or disclosed to any other person or entity except (i) as required by law, (ii) for authorized oversight of the research study, or (iii) for other research for which the use or disclosure of PHI would be permitted by the HIPAA Privacy Rule.

We will attach an Information Sheet (cited above) to the first e-learning invite e-mail, describing the study goals and training phase details, as well as site personnel involvement throughout the duration of the 12-month QI intervention (e-mailed to site personnel just prior to the training phase). Study staff will field any and all questions from potential study subjects prior to their module training and subsequent site meeting.

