**Assessment of Intervention Adoption: Surveys & Rate Feedback**  
*(Selected Vaccine Champions: completion of bi-monthly rate feedback discussions and monthly PDSA cycles and Practice Time & Cost Surveys)*

The assessment of intervention adoption by study sites involves commonly occurring procedures within a medical setting, including the ongoing review of practice metrics (vaccine rate feedback sessions), the development and assessment of practice goals (PDSA Cycles), and the evaluation of personnel efforts to achieve these goals (Time & Cost Survey).

We are therefore seeking a *waiver of documentation of consent and a waiver of HIPAA authorization* for the training portion of the study. More specifically, we are requesting this waiver because: **a)** the assessment portion of the study is no greater than minimal risk, **b)** the purpose of the study/intervention and a description of the assessment tasks will be clearly outlined for vaccine champions in the Information Sheet (see “*InformationSheetVaccineChampion...*” document) e-mailed to them at the onset of the assessment phase, **c)** ample time will be given to each vaccine champion to review the Information Sheet in full and ask questions of study staff regarding the quality improvement effort and/or specific tasks involved in the assessment phase, and **d)** PHI will not be reused or disclosed to any other person or entity except (i) as required by law, (ii) for authorized oversight of the research study, or (iii) for other research for which the use or disclosure of PHI would be permitted by the HIPAA Privacy Rule.

As soon as they are selected, each identified vaccine champion will be e-mailed (see “*VaccineChampionEmail...*” document) an Information Sheet (cited above) by their affiliated study coordinator, outlining the basic study goals as well as their involvement in tasks throughout the training and intervention adoption

phases of the study. After the Information Sheets have been disseminated, study coordinators will conduct a follow-up phone call with each vaccine champion, reviewing their role within the project and fielding any and all questions they may have. The position of vaccine champion is voluntary, and if they do not wish to accept the role, they may decline and another individual will be identified by the affiliated medical director.

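### Section 17 prices personnel cost from study-personnel time and wages only, which conflicts with its own health system perspective and with the practice time collected under Step 4

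*Combined protocol and SAP*

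**What the plan says.** Section 17 (Final Time/Cost Analysis) declares that "we will estimate costs and ICER estimates from the health system perspective". Under Total Cost it adds non-personnel and personnel costs, separates research from intervention personnel cost, and gives practice-level meetings as an example. It then states one pricing rule. Time is "weekly reported by study personnel using a REDCap email survey", and the wage rates are those "by occupation codes of study personnel, derived from the Bureau of Labor Statistics".

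Section 4, Step 4 describes two instruments. The Study Staff Time & Cost Survey is "sent to study personnel on a weekly basis via REDCap". The Practice Time & Cost Survey is "A survey aimed at evaluating the amount of time and money devoted to VAX-MOM intervention activities"; the vaccine champion completes it monthly from best estimates. Table 4 lists a Time/Cost Survey among the sources for implementation outcomes, which include intervention costs, and refers the reader to Step 4.

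Section 7 (Site Personnel Consent) sets out what site personnel do: "completion of e-learning module, attendance of follow-up site meeting, and participation in monthly/bi-monthly discussions of rate feedback and PDSA cycles". Section 17 (Cost-Effectiveness) sets the control-group cost at zero and hypothesises a lower cost per additional vaccination than in similar past interventions. It cites median ICERs of $51 and $125.

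**The concern.** From a health system's viewpoint, staff hours spent on training, feedback meetings and PDSA work are a main resource that a quality improvement programme uses. The plan collects practice time for this purpose, but its only stated pricing rule draws on a different group of people, a different survey and a different set of wages.

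An analyst who follows the rule as written would price study staff's time at a practice meeting but not the attendees' time. An analyst who follows Step 4 would price both. They would report different total costs and ICERs from the same data. Because the control cost is zero, each omitted intervention-arm dollar comes straight off the ICER numerator. With a positive effect, the estimate would look more favourable than a full health-system costing.

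**Working it through.** **1. The passages side by side**

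| | Section 17 formula | Study Staff survey | Practice survey |
|---|---|---|---|
| Reporter | study personnel | study personnel | vaccine champion |
| Frequency | weekly | weekly in Step 4, monthly in Step 2 | monthly |
| Content | time | time and cost | time and money |
| Wage source | study personnel's occupations | as in the formula | none stated |

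The formula fits the Study Staff survey as Step 4 describes it. It fits the practice survey on neither reporter nor frequency.

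Could study personnel include vaccine champions? The term is not formally defined. The text under Table 5 (bi-monthly feedback reports) says "the identified vaccine champions or study personnel will estimate flu and Tdap vaccine rates via manual chart review", which names them as alternatives. Even if champions were included, no time survey is described for the other site personnel.

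**2. Scale**

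The documents state no cost total, wage or ICER for this trial, so there is no cost figure to reproduce. What follows is sensitivity only.

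*Inputs from the documents*
- Power analysis: 6.3-point detectable difference, 5,000 women and 16 practices. I read both as per arm. With ICC 1%, the design effect is 1 + (5,000/16 − 1) × 0.01 = 4.115. At alpha 0.025, power is 80.8% from a 49% base and 81.5% from 54%, which agrees with the stated figure of more than 80%. With 2,500 per arm it would be 70.9% and 71.8%.
- Table 6: 2,100 + 3,235 + 4,481 + 4,600 = 14,416 deliveries in 37 practices, so half is 7,208 in 18.5 practices. Providers: 92 + 73 + 41 + 33 = 239.

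*Assumptions:* the true effect equals 6.3 points, and wages are $25 to $75 per hour.

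*Additional vaccinations of one type*
- (a) Power-section base: 5,000 × 0.063 = 315.
- (b) Table 6 base: 7,208 × 0.063 = 454.1.

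*ICER reduction per $100 of omitted practice time per practice-year, all charged to one vaccine*
- (a) 16 × 100 / 315 = $5.08.
- (b) 18.5 × 100 / 454.1 = $4.07.
- Split equally between two vaccines: $2.54 and $2.04.
- At a 3-point effect: 1,600 / 150 = $10.67 and 1,850 / 216.2 = $8.56.
- At a 10-point effect: 1,600 / 500 = $3.20 and 1,850 / 720.8 = $2.57.

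*One omitted person-hour per practice per month at wage W, 6.3 points*
- (a) 12 × 16 × W / 315 = 0.610W, or $15.24 to $45.71.
- (b) 12 × 18.5 × W / 454.1 = 0.489W, or $12.22 to $36.67.
- Split equally: $7.62 to $22.86 and $6.11 to $18.33.

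*Hours.* The only durations given for practice intervention work are two optional flu boosters of about 15 minutes each, for sites trained before July. For providers alone that is at most 239/37 × 0.5 = 3.2 hours per practice. Nurses and other staff are not counted. The times given for the provider and culture surveys are research measurement, not intervention delivery.

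**The case against.** The strongest reply is that the plan never excludes practice time. The sentence before the formula names practice-level meetings as an intervention cost, Step 4 is headed as the cost evaluation and contains the practice survey, and Step 2 has champions report attendance numbers through it. On that view, section 17 simply mentions one survey where it meant two. The practice survey also asks for money, so some practice cost may already arrive in dollars. The Step 4 figure and the survey form are not available to read, and the visible text does not define the study-arm cost term, so a pricing rule may stand there.

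Most of this stands. A reader might infer that practice hours are deliberately left out of the cost. The documents do not support that: they support a conflict between a formula and its surroundings. What remains is that the one visible pricing rule does not reach practice hours and would need reconciling with any rule stated elsewhere.

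A reader might also infer that the comparison with $51 or $125 is biased or would reverse. That does not follow either. Actual hours and wages are unknown, and the documents do not say whether the benchmark interventions counted practice time. Full assignment and equal split are also not the plan's allocation, which estimates Tdap-specific cost outside flu season and carries it into flu season.

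**Conclusion.** The inconsistency is real and minor. As written, the section 17 rule would omit practice staff hours not already reported in dollars from a cost that claims the health system perspective. Given a zero control cost and a positive effect, total cost and the ICER would be too low.

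The direction rests on the rule being applied as written. The size is unknown: the dollar shifts depend on assumed hours, wages, effect and allocation, and show sensitivity rather than a known error. The primary vaccination comparison does not use this formula.

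**What to change.** Reconcile section 17 with Step 4 and Table 4 by stating:

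- Intervention personnel cost = practice hours from the Practice Time & Cost Survey × Bureau of Labor Statistics wages for the practice occupations + study-staff hours spent on intervention delivery × their own wages.
- If role is not recorded, use an assumed average practice wage and vary it in the one-way sensitivity analyses already planned.
- Count practice costs reported in dollars once. Keep research-only time separate, as already intended.
- If the practice survey does not capture e-learning and site-meeting hours, estimate them from completion and attendance counts and from module or meeting length, and vary that estimate. Tally the counts by role before the individual records are deleted, as sections 14 and 15 provide once credit requests are settled.

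The weekly and monthly descriptions of the Study Staff survey (Steps 4 and 2) can be aligned in the same edit.

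The cost is a few sentences and a little more analysis, largely on data already collected. The ICER will be less favourable than under the present wording.
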